8.5. Pharmacokinetics

Pharmacokinetic parameters are not evaluated in this study.

8.6. Pharmacodynamics

Pharmacodynamics are not evaluated in this study.

8.7. Genetics

8.7.1. Specified Genetics

Genetics (specified analyses) are not evaluated in this study.

8.7.2. Banked Biospecimens for Genetics

Banked Biospecimens for Genetics will not be collected in this study.

8.8. Biomarkers

Biomarkers are not evaluated in this study.

8.9. Medical Resource Utilization and Health Economics

Medical resource utilization and health economics parameters are not evaluated in this study.

9. STATISTICAL CONSIDERATIONS

9.1. Estimands and Statistical Hypotheses

9.1.1. Estimands

Only discontinuation of study intervention will be considered as an intercurrent event.

9.1.1.1. Primary Estimand/Co-Primary Estimands

Estimand 1: The primary estimand of this study is a while-on-treatment estimand, which estimates the treatment effect of crisaborole compare with vehicle at Week 6 /EOT. It includes the following 5 attributes:

- Population: participants ≥ 45 years of age with SD without active skin ulceration;
- Variable: non-longitudinal endpoints at Week 6/EOT;
- Treatment condition: crisaborole 2% BID or vehicle;

- Intercurrent event: all data after an intercurrent event of discontinuation of study intervention will be excluded, data at Week 6/EOT will be included;
- Population-level summary: difference in LSM for continuous endpoints and difference in proportion of participants with response for binary endpoints at Week 6/EOT between crisaborole ointment, 2%, BID and vehicle.

Estimand 1 will be used in analyzing the primary endpoint and it will also be used to analyze non-longitudinal continuous secondary endpoints %BSA in-person assessment **CCI** [REDACTED] and non-longitudinal binary endpoints ISGA success and ISGA clear/almost clear in-person assessment.

9.1.1.2. Secondary Estimands

Estimand 2: The second estimand of this study is a composite estimand, which estimates the treatment effect of crisaborole compared with vehicle at each time point. It includes the following 5 attributes:

- Population: participants ≥ 45 years of age with SD without active skin ulceration;
- Variable: binary response endpoint per photography assessment, eg, response defined as a participant with an ISGA score of Clear (0) or Almost Clear (1) with at least a 2-grade improvement from baseline at each time point; a participant after an intercurrent event of discontinuation of study intervention will be considered a non-responder for the visit of interest;
- Treatment condition: crisaborole 2% BID or vehicle;
- Intercurrent event: there will be no intercurrent event since the discontinuation of study intervention is part of the variable definition;
- Population-level summary: difference in proportion of participants with response at each time point between crisaborole ointment, 2%, BID and vehicle.

Estimand 2 will be used in analyzing all applicable longitudinal secondary binary endpoints. Estimand 3: The third estimand of this study is a hypothetical estimand, which estimates the treatment effect of crisaborole compared with vehicle at each time point under the scenario of no discontinuation of study intervention. It includes the following 5 attributes:

- Population: participants ≥ 45 years of age with SD without active skin ulceration;
- Variable: percent change from baseline in TSS at each time point;
- Treatment condition: crisaborole 2% BID or vehicle;
- Intercurrent event: all data after any intercurrent events will be excluded;

- Population-level summary: difference in mean percent change from baseline in TSS at each time point between crisaborole ointment, 2%, BID and vehicle.

Estimand 3 will be used in analyzing the longitudinal continuous endpoints.

9.1.2. Multiplicity Adjustment

There is no multiplicity adjustment.

9.2. Sample Size Determination

The primary efficacy analysis is to compare the mean difference in percent change from baseline in TSS at Week 6 of crisaborole ointment, 2%, BID versus vehicle based on HVP home visit in person assessment. A sample size of 35 participants per treatment group will yield at least 80% power to detect a difference between crisaborole ointment, 2%, BID and vehicle at a one-sided significance level of 5%, assuming a mean difference of at least 22% and a common standard deviation of no more than 35% based upon clinical trial data of crisaborole in AD participants.

9.3. Populations for Analyses

For purposes of analysis, the following populations are defined:

Participant Analysis Set	Description
Screened	All participants who sign the ICF.
Enrolled	All participants who sign the ICF and are not screen failure.
Randomly Assigned to Study Intervention	All participants who are randomized.
Full Analysis Set (FAS)	All participants who are randomly assigned to study intervention and apply at least 1 dose of study intervention. Participants will be analyzed according to the intervention they are randomized.
Safety Analysis Set (SAF)	All participants who are randomly assigned to study intervention and apply at least 1 dose of study intervention. Participants will be analyzed according to the intervention they actually received.
Full Analysis Set-Interim Analysis (FAS-IA)	All participants who are randomly assigned to study intervention and apply at least 1 dose of study intervention and complete 6 weeks treatment or early discontinue study intervention at the IA cutoff date. Participants will be analyzed according to the intervention they are randomized.
Safety Analysis Set-Interim Analysis (SAF-IA)	All participants who are randomly assigned to study intervention and apply at least 1 dose of study intervention and complete 6 weeks treatment or early discontinue study intervention at the IA cutoff date. Participants will be analyzed according to the intervention they actually received.

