
To evaluate the safety and local tolerability of crisaborole ointment, 2%, BID versus vehicle in participants with SD without active skin ulceration.	
Incidence and severity of treatment emergent adverse events, including local tolerability events.
Estimands	
Only discontinuation of study intervention will be considered as an intercurrent event.	
The primary estimand of this study is a while-on-treatment estimand, which estimates the treatment effect of crisaborole compared with vehicle at Week 6 or EOT. It includes the following 5 attributes:	

Population: Participants \geq45 years of age with SD without active skin ulceration;Variable: non-longitudinal endpoints at Week 6/EOT;Treatment condition: crisaborole 2% BID or vehicle;Intercurrent event: all data after an intercurrent event of discontinuation of study intervention will be excluded, data at Week 6/EOT will be included;Population-level summary: difference in LSM for continuous endpoints and difference in proportion of participants with response for binary endpoints at Week 6/EOT between crisaborole ointment, 2%, BID versus vehicle.	
See Section 9.1.1 for additional information on estimands.	

Overall Design:

This is a Phase 2a, randomized, double-blind, vehicle-controlled, parallel-group, proof-of-concept study enrolling approximately 70 eligible participants randomized into the double-blind treatment period in a 1:1 ratio to receive BID crisaborole ointment 2% or vehicle for 43 days.

The total duration of participation in the study is up to 14 weeks, including up to 4 weeks for screening, a 6-week double-blind treatment period, and follow-up period of 4 weeks after treatment completion.

Disclosure Statement:

This is a Parallel Treatment study with 2 Arms that is Sponsor, Investigator and Participant blinded.

Number of Participants:

Approximately 70 participants will be randomized.

Intervention Groups and Duration:

[figure not shown]
Group 1 (N=35): Crisaborole ointment, 2% (w/w) BID for 43 days

Group 2 (N=35): Vehicle BID for 43 days

Data Monitoring Committee:

An IRC will be utilized if an IA is performed

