9.5. Interim Analyses

An IA may be performed to assess efficacy and safety after approximately 50 participants complete 6 weeks treatment or early discontinue study intervention. If an IA is performed, IA results will be used for decisions regarding stopping for futility and planning for future studies. There is no efficacy claim and no sample size adjustment based on the IA results.

Participants may be discontinued from the study as a result of the IA, as described in [Section 7](#).

This is an administrative interim analysis; no adjustment of p-values is planned for the analysis of the final study data.

Before the IA is performed, the details of the objectives, decision criteria, dissemination plan, and method of maintaining the study blind as per Pfizer's SOPs will be documented and approved in an IRC charter. In addition, the analysis details will be documented and approved in a SAP. The results of the IA will not be shared with the study team, sites, or participants during the conduct of the study, except in a situation where the IRC recommends early termination of the study.

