10.1.5. Committees Structure

10.1.5.1. Data Monitoring Committee (DMC)

If an IA is performed, the IRC will be responsible for review of the IA and recommendation on any changes to study conduct based on the results of the IA according to the IRC

Charter. Safety data and efficacy results will be reviewed by the IRC during study conduct if an IA is performed. The recommendations made by the IRC will be forwarded to the appropriate authorized Pfizer personnel for review and final decision. Pfizer will communicate such decisions, which may include summaries safety data, to regulatory authorities, investigators, as appropriate.

This study will not use an external DMC.

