6.6. Safety Summaries and Analyses

Safety analyses will be summarized in accordance with Pfizer Data Standards.

All clinical AEs, SAEs, TEAEs, withdrawal due to AEs, will be reviewed and summarized on an ongoing basis during the study to evaluate the safety of participants.

Safety data will be presented in tabular and/or graphical format and summarized descriptively, where appropriate. All safety endpoints will be listed and summarized in accordance with Pfizer Standards. Categorical outcomes (eg, AEs) will be summarized by participant counts and percentage. Continuous outcome (eg, pulse rate, etc) will be summarized using n, mean, median, standard deviation, etc. Participant listings will be produced for these safety endpoints accordingly.

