7. INTERIM ANALYSES

An IA may be performed to assess efficacy after approximately 50 participants complete 6 weeks treatment or early discontinue study intervention. Interim analysis results will be used for decisions regarding stopping for futility and planning for future studies.

All study personnel and sponsor's staff involved with this study will remain blinded to individual subject data for interim analysis.

A third party Pfizer programmer/biostatistician who is unrelated to the study team will conduct the interim analysis. The third party will receive the unblinded treatment codes from clinical pharmacy and make the appropriate changes to the analysis programs prepared by the clinical programmer and study biostatistician in the **CCI** [REDACTED]. After successful execution of

all interim analysis programs, the third party will place the results in **CCI**. An **CCI** folder containing summary data will be created and protected such that only designated persons can gain access.

The decision criterion is based on the primary endpoint. The efficacy will not be claimed based on this interim analysis. If the efficacy criterion is met, the study will continue and remain blinded to study personnel until the final database unblinding, and phase 3 studies can start planning. The final analysis will be performed at the final official database release. If futility criterion is met, this study will be terminated.

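### If an interim analysis is run, its by-arm safety tables omit dosed participants still on treatment, because SAF-IA carries over the completion-or-discontinuation condition of FAS-IA

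*Protocol*

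**What the plan says.** Protocol 9.3 and SAP Section 4 define SAF-IA in the same words. A participant must be randomized and have applied at least one dose, with this further condition and rule for assignment to arm: "complete 6 weeks treatment or early discontinue study intervention at the IA cutoff date. Participants will be analyzed according to the intervention they actually received". FAS-IA in the same tables has the same entry conditions; the two sets differ only in whether participants are assigned to arm as treated or as randomized. The final safety set has no completion condition: "All participants who are randomly assigned to study intervention and apply at least 1 dose of study intervention".

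On the purpose of the interim analysis, Protocol 9.5 says: "An IA may be performed to assess efficacy and safety after approximately 50 participants complete 6 weeks treatment or early discontinue study intervention". Protocol 10.1.5.1 adds: "Safety data and efficacy results will be reviewed by the IRC during study conduct if an IA is performed", and also "This study will not use an external DMC". SAP Section 7 gives the purpose without safety: "An IA may be performed to assess efficacy after approximately 50 participants complete 6 weeks treatment or early discontinue study intervention".

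Outside the interim analysis, SAP 6.6 says that adverse events, serious events and withdrawals due to adverse events "will be reviewed and summarized on an ongoing basis during the study to evaluate the safety of participants". That text is not tied to the IRC, to treatment arm or to an analysis set.

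**The concern.** The completion condition has a reason in FAS-IA: the primary endpoint is read at Week 6/EOT, so a participant in mid-treatment has nothing to contribute. That reason does not carry over to safety. Protocol 8.3.1 collects adverse events from consent to at least 28 days after the last dose, and the schedule in 1.3.2 asks for them at every contact. Data on participants still in treatment therefore exist at the cutoff, but the set definition removes both their events and their person-time.

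Two things follow for the interim tables:

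- **Omission.** An event in someone still applying ointment is in neither the numerator nor the denominator of the by-arm summaries.
- **Selection.** A recent starter can enter SAF-IA only by stopping early. Those who started alongside and are still on treatment are left out. Discontinuation, and events that lead to it, are therefore over-represented.

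What is at stake is the accuracy of the by-arm safety comparison that the SAP would supply to the IRC, in a trial with no external data monitoring committee.

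**Working it through.** **Set definitions side by side**

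| Set | At least 1 dose | Completed 6 weeks or stopped by cutoff | Assigned to arm |
|---|---|---|---|
| FAS-IA | yes | required | as randomized |
| SAF-IA | yes | required | as treated |
| SAF (final) | yes | not required | as treated |

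No other interim safety set is defined in either document.

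**Plan's own figure.** The plan gives no figure for this point. The sample size statement in Protocol 9.2 (35 per arm, difference 22, standard deviation 35, one-sided 5%) reproduces: 22 / (35 × √(2/35)) = 2.63, and Φ(2.63 − 1.645) = 83.8%, against a stated minimum of 80%. Nothing below changes it.

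**Number omitted.** Inputs are the interim trigger of about 50 ended treatments (Protocol 9.5) and the total in Protocol 1.1: "Approximately 70 participants will be randomized".

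- Omitted = dosed at cutoff − about 50.
- Lower limit: 50 − 50 = 0.
- Upper limit: 70 − 50 = 20, and 20/70 = 28.6% of those dosed.

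**Position within that range.** This depends on accrual, which is not in the documents. With a treatment period of about 6 weeks and a steady start rate r per week, about 6r participants are on treatment at the cutoff, capped at 20. Early stopping lowers this slightly. The rates are assumptions.

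| Assumed starts per week | On treatment at cutoff | Share of those dosed |
|---|---|---|
| 0.5 | 3 | 3/53 = 5.7% |
| 1 | 6 | 6/56 = 10.7% |
| 2 | 12 | 12/62 = 19.4% |
| 3 | 18 | 18/68 = 26.5% |
| 4 | 20 (cap) | 20/70 = 28.6% |

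**Chance that the omitted group contains an event.** For true rate p and k omitted, the chance of at least one case is 1 − (1 − p)^k.

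| Assumed rate p | k = 6 | k = 12 | k = 20 |
|---|---|---|---|
| 5% | 26% | 46% | 64% |
| 2% | 11% | 22% | 33% |

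These are upper bounds: p is a full-course rate and the omitted participants have only partial exposure.

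**Over-representation of early stoppers.** A simulation used random (Poisson) starts at an assumed 1 to 8 per week, stopping times uniform over the 6 weeks, and a cutoff at the 50th ended treatment. The proportion of discontinuers inside SAF-IA averaged about 10.6% to 13.0% when the true full-course rate was 10%, and about 21% to 26% when it was 20%. The distortion grows with the accrual rate.

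**The case against.** There is a good case that this is minor, and most of it stands.

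- **The interim analysis is optional and SAF-IA drives no stated decision.** It is administrative, for futility and planning, and SAP Section 7 puts the decision criterion on the primary endpoint. No interim safety boundary is given. This stands.
- **Participants are monitored by other routes.** SAP 3.5 has investigators and sponsor clinicians reviewing individual data throughout. SAP 6.6 provides ongoing adverse event review, and Protocol 8.3.1.1 requires serious events to be reported within 24 hours. This stands. A reader might infer from the set definition that nobody is watching participants still on ointment; the documents say otherwise.
- **An analysis set is not everything the IRC sees.** Protocol 10.1.5.1 gives the IRC safety data without restriction, and Protocol 9.5 leaves the details to a charter that is not among the documents. A reader might infer that the IRC's whole safety review excludes on-treatment participants. The text supports this only for tables built on SAF-IA. Wider listings would help, but would not correct the denominators of those tables.
- **An all-dosed set mixes exposures.** It combines completers, early stoppers and participants in mid-treatment, so crude incidence is harder to read. The final set already mixes the first two groups, so mixing alone is no argument against SAF-IA. Limiting crude percentages to ended treatments is defensible, but it brings the selection shown above. Reporting exposure by arm deals with this better than dropping participants.
- **The SAP names efficacy but does not exclude safety.** It also defines SAF-IA, so interim safety summaries are evidently intended. The difference from Protocol 9.5 is a wording mismatch and does not make the point more serious.

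**Conclusion.** The point holds for the interim by-arm safety tables. As defined in both documents, SAF-IA omits dosed participants still on treatment and over-represents early discontinuers, although the protocol makes safety part of the interim analysis and of the IRC review.

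The documents alone support a count of 0 to about 20 of about 70, at most 28.6%. Any narrower figure rests on an assumed accrual rate. The number is small if accrual is slow, and reaches the cap only if all of the roughly 70 have been dosed by the cutoff.

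The final safety analysis, the primary analysis, power and the significance level are unaffected. A reader might treat the interim review as the trial's one safeguard and so rate this as a must-fix. The documents do not support that: the review may never take place, its stated criterion is efficacy, and participant-level monitoring runs throughout. This is a cheap improvement that should be made before any interim analysis is run.

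**What to change.** 1. In Protocol 9.3 and SAP Section 4, define SAF-IA as all randomized participants who applied at least one dose on or before the interim cutoff, analysed by treatment received, using all adverse event data up to the cutoff.
2. Keep the completion-or-discontinuation condition for FAS-IA only.
3. In SAP Section 7, state the purpose as efficacy and safety, to match Protocol 9.5.
4. Show exposure time by arm next to the interim adverse event counts, because crude incidence will now include participants with partial exposure.

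The cost is one definition in each document, one phrase in the SAP, a changed filter in the interim programs and an exposure summary. No participants, visits or alpha are involved. The small downside is the partial exposure in item 4: crude percentages will tend to understate full-course incidence and should be read with the exposure figures.

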9.4. Statistical Analyses

The SAP will be developed and finalized before any analyses are performed and will describe the participant populations to be included in the analyses, and procedures for

accounting for missing, unused, and spurious data. This section is a summary of the planned statistical analyses of the primary and secondary endpoints.

9.4.1. General Considerations

In general, number, percent and 90% CI will be presented for binary endpoints. Descriptive summary statistics (n, Mean, Standard deviation, Median, Min., Max.) will be presented for continuous endpoints. In addition, graphics may be used to present the data.

Day 1 will be the date when a participant applies the first dose of study intervention. Baseline value will be the last non-missing assessment on or before Day 1 and prior to first dose of study intervention. **CCI**

9.4.1.1. Analyses for Binary Endpoints

For binary endpoint at each time point, large sample approximation to the difference in binomial proportions will be used for testing (Normal Z-test) the superiority of crisaborole ointment, 2%, BID to vehicle and for forming 90% CI's and calculating p-values (one-sided).

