5.1. Inclusion Criteria

Participants are eligible to be included in the study only if all the following criteria apply:

Age

1. Participant must be ≥ 45 years of age at the time of signing the informed consent.

Type of Participant and Disease Characteristics

2. Participants who have SD:

- A known diagnosis of SD based upon HCP medical records for at least 3 months prior to screening with inadequate response to current treatment. Inadequate response is defined by ISGA ≥ 2 (range 0-4) and TSS ≥ 3 (range 0-12) at the screening visit;

OR

- Newly diagnosed by the Investigator based upon the following:
 - a. Participant confirmation of symptoms present on lower extremities for at least 3 months prior to screening;
 - b. HVP complete physical examination findings;
 - c. Telemedicine assessment by the Investigator;
 - d. Inadequate response to current treatment. Inadequate response is defined by ISGA ≥ 2 (range 0-4) and TSS ≥ 3 (range 0-12) at the screening visit.
- Active unilateral or bilateral SD lesions on the lower extremities (from knee to ankle and dorsum of foot) and the involved areas total $\geq 1\%$ BSA (1 handprint of the participant) at the screening visit.

Sex

3. Male or Female

Informed Consent

4. Capable of giving signed informed consent as described in [Appendix 1](#) which includes compliance with the requirements and restrictions listed in the informed consent form (ICF) and in this protocol.

Other

5. Participant's mental and physical status allows them to be able to mostly perform their activities of daily living with minimal assistance including the ability to:
 - a. Apply ointment to the lower part of their legs;
 - b. Comply with compression therapy, if worn prior to screening;
 - c. Comply with study procedures, including home visits, digital imaging and image capture;
 - d. Comply with use of an internet-enabled device, (eg smartphone, tablet, laptop or desktop computer) to complete patient-reported outcome assessments (PROs), and the dosing diary.

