6.3. Measures to Minimize Bias: Randomization and Blinding

Study using IRT	All participants will be centrally assigned to randomized study intervention using an Interactive Response (IRT) Technology System. Before the study is initiated the log in information & directions for use of the IRT will be provided to the Investigator and appropriately trained designees. Study intervention will be dispensed as summarized in Schedule of Activities .
-----------------	------------------------------------------------------------------------------------------------------------------------------------------------------------------------------------------------------------------------------------------------------------------------------------------------------------------------------------------------------------------------------------------------------

	Returned study intervention should not be re-dispensed to the participants.
Blind Break (IRT)	
The IRT will be programmed with blind-breaking instructions. In case of an emergency, the investigator or sponsor has the sole responsibility for determining if unblinding of a participant's treatment assignment is warranted. Participant safety must always be the first consideration in making such a determination. If the investigator decides that unblinding is warranted, the investigator should make every effort to contact the sponsor prior to unblinding a participant's treatment assignment unless this could delay emergency treatment of the participant. If a participant's treatment assignment is unblinded, the sponsor must be notified within 24 hours after breaking the blind. The date and reason that the blind was broken must be recorded in the source documentation and case report form, as applicable.
 
An IA may be performed during the conduct of the study. Participants or study sites will not be unblinded as a result of a meeting a futility threshold.

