9.4.3. Secondary Endpoints/Estimands Analysis

Percentage change from baseline in %BSA at Week 6/EOT based on in-person assessment will be analyzed using an ANOVA model that includes treatment group as a factor (see [Section 9.4.1.2](#)) based on Estimand 1 using FAS.

Achievement of an ISGA success and ISGA clear/almost clear at Week 6/EOT based on in-person assessment will be analyzed using the method described in [Section 9.4.1.1](#) using Estimand 1 and FAS.

Percent change from baseline in TSS and %BSA based on Central Readers assessments will be analyzed using MMRM as described in [Section 9.4.1.2](#). Missing data are assumed MAR. Under MAR assumption, MMRM will yield unbiased estimates and valid inferences for treatment effects assuming all participants maintain therapy. This analysis will be based on Estimand 3 using FAS.

Achievement of an ISGA success and ISGA clear/almost clear by time point based on Central Readers assessments will be analyzed using the method described in [Section 9.4.1.1](#). Observations after the discontinuation of study intervention or missing values for any reason will be handled by setting the endpoint to nonresponsive. Note that this is a composite endpoint in the sense that a response requires the participant completes a visit of interest eg, Week 6, and achieves a response per the defined response criteria (otherwise it is considered a nonresponse). This method of handling missing response is known as missing response as non-response (MR-NR). The analysis will be based on Estimand 2 using FAS.

CCI

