3.2. Secondary Endpoints

The secondary endpoints are:

- Achievement of an ISGA score of Clear (0) or Almost Clear (1) with at least a 2-grade improvement from baseline at all time points (analyze both HVP in-person assessment and Central Readers digital images assessment).
- Achievement of an ISGA score of Clear (0) or Almost Clear (1) at all time points (analyze both HVP in-person assessment and Central Readers digital images assessment).
- Percent change from baseline in TSS at all time points (Central Readers digital images assessment).
- Percent change from baseline in lesional %BSA at all time points (analyze both HVP in-person assessment and Central Readers digital images assessment).

CCI

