6.2.2. ISGA Success at Week 6/EOT based on In-person Assessment

- Estimand strategy: while-on-treatment, Estimand 1 ([Section 2.1.2](#))
- Analysis set: FAS ([Section 4](#))
- Variable: ISGA success at Week 6/EOT based on in-person assessment
- Analysis method: Normal approximation to binomial
- Intercurrent event: all data after an intercurrent event of discontinuation of study intervention will be excluded, data at Week 6 or EOT will be included;
- P-value from normal approximation test, the estimate of proportion, difference in proportion and the corresponding 90% CI of participants with response at Week 6/EOT between crisaborole ointment, 2% versus vehicle will be presented. Proportions of response (\pm SE) will also be presented graphically by treatment group.

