6.4. Subset Analyses

Percentage change from baseline in TSS, ISGA success, ISGA clear/almost based on HVP in-person assessment will be analyzed by subgroups of type of standard of care, skin type, baseline ISGA, disease duration (by median), age (≤ 64 vs ≥ 65), race (White vs Non-white).

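### ISGA clear/almost clear is tested without adjustment for baseline ISGA, which sets how many grades a participant must improve; stratifying is a cheap improvement for this secondary endpoint

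*Protocol*

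**What the plan says.** - Protocol 9.4.1.1, repeated in SAP 5.2.2, sets one method for every binary endpoint: a "large sample approximation to the difference in binomial proportions will be used for testing (Normal Z-test) the superiority" of crisaborole, with a one-sided p-value and a 90% CI. No stratum or covariate is named, and the text does not say whether the variance is pooled.
- Protocol 9.4.3 applies it to the in-person endpoints: "Achievement of an ISGA success and ISGA clear/almost clear at Week 6/EOT based on in-person assessment will be analyzed using the method described in" that section. The image-based endpoints refer to the same method.
- SAP 6.2.2 has "Analysis method: Normal approximation to binomial"; SAP 6.2.1, 6.2.3, 6.2.4 and Appendix 1 agree.
- SAP 3.2 defines two responder endpoints: ISGA success ("Achievement of an ISGA score of Clear (0) or Almost Clear (1) with at least a 2-grade improvement from baseline at all time points") and clear/almost clear ("Achievement of an ISGA score of Clear (0) or Almost Clear (1) at all time points").
- Protocol 5.1 requires ISGA of at least 2 at the screening visit, on a 0-4 scale.
- Baseline ISGA is a listed baseline variable (SAP 3.4). Its only analytic role is in SAP 6.4, where in-person TSS and ISGA results "will be analyzed by subgroups of type of standard of care, skin type, baseline ISGA" and other factors.
- On allocation, Protocol 6.3 says "All participants will be centrally assigned to randomized study intervention using an Interactive Response (IRT) Technology System". Protocol 6.2 mentions a randomization list. Neither names a stratification factor.

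**The concern.** For clear/almost clear, the starting grade fixes the distance to response: 1 grade from a baseline of 2, 2 grades from 3, 3 grades from 4. Unless sicker participants improve by correspondingly more grades, the chance of response falls as baseline rises.

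With about 35 per arm, the mix of starting grades may differ between arms by chance. A raw difference in proportions carries that imbalance into the estimate, and the variation that baseline explains stays in the error term. Protocol 9.4.1.2 allows baseline covariates for continuous endpoints, but there is no equivalent for the responder endpoint whose definition depends most directly on baseline. At stake is the width of the interval for a secondary estimate that later studies may use in planning.

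**Working it through.** **The plan's own figure.** The only power statement is for the primary TSS endpoint (Protocol 9.2): 35 per arm, difference 22, SD 35, one-sided 5%. The SE is 35 x sqrt(2/35) = 8.37; 22/8.37 - 1.645 = 0.985; power is 83.8% (83.1% with the t distribution). This agrees with at least 80%. No power or response rate is given for ISGA, so every rate below is an assumption.

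**Size of chance imbalance.** If a share p starts at ISGA 2 and allocation is not stratified by ISGA, the SD of the between-arm difference in that share is sqrt(2p(1-p)/35): 0.114 at p = 0.35, 0.120 at p = 0.50, 0.110 at p = 0.70. At p = 0.40 the arms differ by 4 or more participants (4/35 = 11 points) in about 39% of trials, and by 20 points or more in about 11%.

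**Effect on the estimate.** The shift is roughly the imbalance times the gap in response between strata. A 10- to 20-point imbalance moves the difference by 1-2 points at a 10-point gap, 2.5-5 at 25 and 4-8 at 40. For comparison, with 25% vs 45% responding, the SE is sqrt(0.25 x 0.75/35 + 0.45 x 0.55/35) = 0.111, a 90% half-width of 1.645 x 0.111 = 18 points. With 15% vs 35% these are 0.101 and 17 points.

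**Effect of stratifying clear/almost clear.** Simulated trials had 35 per arm, simple randomization and no dropout. Variance ratio means the Mantel-Haenszel difference over the raw difference, under a treatment effect.

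| Assumed role of baseline ISGA | Variance ratio | One-sided 5% power, raw to stratified |
|---|---|---|
| Weak: vehicle 28/22/18% from baseline 2/3/4 (a) | 1.03 | 71 to 69% |
| Moderate: 35/20/10% (a) | 0.98 | 68 to 68% |
| Moderate: 40% chance of one extra grade of improvement per higher baseline grade (b) | 0.95-0.98 | -0.7 to +1.9 points |
| Strong: 45/20/5% (a) | 0.91 | 65 to 66% |
| Strong: grade change independent of baseline (b) | 0.84-0.92 | +1.7 to +7.0 points |
| Extreme: 60/15/2% (a) | 0.76 | 52 to 59% |

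(a) Baseline mix 40/50/10% (50/40/10% in the extreme case), log odds ratio 1.1, three strata, unpooled Z against the Cochran-Mantel-Haenszel test, 40,000 runs. (b) Two strata (2 vs >=3), Sato variance, pooled Z as comparator in the independent-change row. That row assumes vehicle rates of 55/20/3% or 40/12/2%, crisaborole rates of 75/38/8% or 62/26/6%, and 35-70% starting at ISGA 2, with 20,000 runs per scenario. The extra-grade row relaxes the independence assumption, with 40,000 runs.

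The largest gain in the independent-change row, 40.8 to 47.8%, depends partly on the comparator. A rerun of that scenario gave 40.7% pooled, 43.0% unpooled and 47.3% stratified, so about 2 of the 7 points come from the variance formula.

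**In interval width.** Width scales with the square root of the ratio: sqrt(1.03) = 1.015, sqrt(0.92) = 0.96, sqrt(0.84) = 0.92, sqrt(0.76) = 0.87. An 18-point half-width becomes 18.3, 17.3, 16.5 and 15.7 points.

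**Error under the null, clear/almost clear.** In the (a) scenarios the planned test rejects in 5.3-5.6% of trials unpooled and 4.7-5.3% pooled, against 4.9-5.1% for Cochran-Mantel-Haenszel. Under independent grade change it is 4.9-5.7% for the pooled Z-test and 5.2-5.5% for the stratified test.

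**ISGA success.** Baseline 2 must reach 0 (2 grades), baseline 3 must reach 1 (2 grades) and baseline 4 must reach 1 (3 grades). With grade change independent of baseline, stratifying raises the variance by 1-2%.

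**The case against.** The strongest reply is that nothing planned is invalid. That stands. A reader might infer that chance imbalance biases the comparison, but under randomization the raw difference is unbiased on average, and its CI and test already allow for such imbalance. The small excess over 5% with unpooled variance also appears when baseline is only weakly prognostic, so it comes from the small-sample approximation.

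A reader might also infer that randomization is unstratified. The documents only name no factor. If the list is stratified by ISGA, the imbalance point largely falls away, though the analysis should then reflect the stratum.

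A third tempting reading is that both ISGA endpoints lose precision. For ISGA success the definition does not force it, because baselines 2 and 3 need the same drop. A gain there needs a sharp assumed contrast: vehicle success of 5% from baseline 2 against 30% from baseline 3 gives a ratio of 0.88, while weaker contrasts give 0.98 to 1.03.

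Nor does entry at ISGA 2 or more mean that everyone has an analysis baseline of 2 to 4. The criterion applies at screening, baseline is the last pre-dose value, and the Central Reader scores separately, so baselines of 0 or 1 are possible.

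Finally, the stakes are modest: a secondary endpoint without multiplicity control in a proof-of-concept trial, with in-person results already shown by baseline ISGA. Subgroup tables will make an imbalance visible, but they do not give an adjusted overall estimate. Choosing one after seeing an imbalance would be post hoc.

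**Conclusion.** The point holds as a cheap improvement to one secondary endpoint, ISGA clear/almost clear. The analysis leaves out a baseline value that is already collected and that determines the improvement required.

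The size depends on how prognostic baseline ISGA proves to be, which the documents do not tell us. Stratifying could cost about 3% in variance, save 2-5% or 8-16%, or save about 24% in an extreme case. Power moves by about -2 to +7 points. The 8-16% range requires grade change to be independent of baseline and should not be read as the expected gain. All figures assume 35 analysed per arm, and baselines of 0 or 1 were not modelled.

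The documents do not support a claim of bias, an invalid test, or a precision loss in ISGA success that follows from its definition.

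**What to change.** For ISGA clear/almost clear, amend Protocol 9.4.1.1 and SAP 5.2.2, 6.2.3, 6.2.4 and Appendix 1 before unblinding:

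- Main analysis: Mantel-Haenszel risk difference stratified by baseline ISGA (<=2 vs >=3), Sato variance, with the same one-sided 5% test and 90% CI. Grade 4, likely to be sparse, is pooled with 3; any baseline of 0 or 1 falls in the lower stratum.
- Baseline from the same rater type: HVP for in-person, Central Reader for images. If no gradable image baseline exists, the HVP baseline assigns the stratum.
- Unstratified difference reported as supportive.
- ISGA success (SAP 6.2.1, 6.2.2) left as planned.

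The summary measure remains a difference in proportions. With near-equal arms, the weight n1 x n0/(n1 + n0) is close to proportional to stratum size, so the target hardly moves. The cost is SAP and protocol wording and a few lines of code, with no new data. The downside is up to about 3% more variance if baseline ISGA is only weakly prognostic.
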